3.1. Participant population

The primary analysis is an intention to treat (ITT) analysis, based on the assumption that all participants enrolled at baseline will be followed up over the study period and all participants included in the final analysis, and the analysis will be done according to the group they were allocated to, disregarding if they received the intervention.

A small number of participants will be excluded from the analysis. Specifically, if they: 1) were enrolled in school at baseline, 2) if they double-enrolled in the study, 3) if they did not provide primary outcome data at baseline.

3.2. Levels of confidence and p-values

Statistical tests and confidence intervals will be two-sided. The statistical significance level set will be at the 5% level. P-values, confidence intervals and standard errors will be provided.

3.3. Unadjusted and adjusted analysis

All comparative analyses will allow for the clustered nature of the data to ensure correct confidence intervals and type I error rates are calculated. As the trial includes at least 34 clusters, the analyses will be based on the individual-level summarized data. For each outcome, unless otherwise specified, the primary analysis will be the covariate-adjusted analysis, with the statistical models including the stratification variables and baseline values for the outcome under consideration, where available.

Adjustment for baseline covariates is often advised firstly to correct for any chance imbalances in important baseline variables following randomization, and secondly, because adjusting for highly important baseline variables in an RCT can improve the precision of treatment effect estimates even when the outcome measure is binary. Statistical testing for baseline imbalances is not advised and instead key covariates should be selected prior to analysis based on the likely magnitude of the association with the

outcome measure (European Agency for the Evaluation of Medicinal Products, 2003). We have, however, looked at whether there were meaningful differences at baseline by looking at standardized mean differences. We will also perform a multivariable logistic regression to consider any imbalance that may occur in important baseline characteristics known to predict IPV outcomes between the groups using the following variables:

- Baseline term for variable
- Controlling behaviors
- Food insecurity
- Any earnings in past month (none or R1 or more)
- Childhood trauma
- Age
- Education
- Alcohol use

This selection of variables is based on baseline analysis of the data predicting past year physical and/or sexual IPV. Time will also need to be adjusted for since intervention and control clusters were not measured concurrently.

Odds ratios will be quoted together with their 95% confidence intervals and exact P-values. Generalized estimating equations will be used to account for the clustered-nature of the data in the primary analysis (**Section 3.5.1**).

3.4. Missing data

The population is highly mobile and the likelihood of participation retention being less than optimal is likely. To deal with completely missing cases (as opposed to items/variables) a rule has been set in place. If the missing data is $\leq 25\%$ we will use multiple imputation with random-effects logistic regression model approach (Stata v15.1). If there is $>25\%$ missing cases, we will use inverse probability weighting to deal with missing data [refs].

At the individual level, because of data collection techniques, missing data is highly unlikely (in the baseline it was $<1\%$) and as such, we will not impute.

3.5. Proposed Analyses

3.5.1. Primary analysis of primary outcomes

As described above, the primary analysis of the primary outcomes, will follow an intention-to-treat approach, with individuals analyzed according to the trial group to which their settlement was randomized. Since the clusters vary between 17-22 clusters between arms, we will conduct individual-level analysis, as it will be statistically more efficient and allow analysis of the effects of individual-level covariates. Mixed effects models will be used for quantitative outcomes i.e. continuous response variables, to take account of between-cluster variation. For binary outcomes, generalized estimating equations (GEE) will be used with an exchangeable correlation matrix and robust standard errors. GEE performs well for binary data more than the logistic regression random effects model and allow for clustering effects by assuming observations in the same cluster are correlated [Hayes & Moulton, 2017].

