### 7.7.1 Sample size calculation:

In the pilot study conducted in 2012-13 the past year prevalence of physical and/or sexual IPV perpetration and victimisation was 45% among men and 41% among women. These levels of violence are exceptionally high by South African standards, so we have modelled the sample size on a range of possible baseline rates (see the table). The sample size assumes 14 will be followed up per cluster (of the 20), but figures are robust to a follow up of only 12 in each cluster. Assuming a coefficient of variation  $k=0.2$  and modelling 80% power. The table shows that with 14 male (and 14 female) participants per cluster and 16 clusters we will have power to detect a range of possible incidence and impact scenarios and to analyse men and women separately (see table). Our power will be further enhanced by having multiple assessments and an additional two clusters.

IPV incidence (12 months)			# of clusters required by arm
11	12	power	
36	29	80	16
45	36	80	15
41	33	80	16
24	19	80	14
18	14	80	13
30	24	80	15

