2.1. Study overview

The Stepping Stones and Creating Futures intervention trial is a cluster randomized control trial (CRT), with two arms and is open label. The study population are out-of-school young women and men aged 18-30 (at baseline), resident in informal settlements, and without formal employment. 34 clusters were identified, using both naturally-occurring clusters and researcher-imposed clusters, and then randomized 1:1 by a statistician, blinded to cluster names using numbers.

Because of practical reasons, 16 control clusters had data collected September 2015-December 2015, while 1 control cluster had data collected in August 2016. Phase 1 intervention clusters had data collected January 2016-February 2016, with the intervention delivered until June 2016. Phase 2 intervention clusters had data collected August 2016 – September 2016, with the intervention delivered from then - February 2017. In total 680 women and 677 men were recruited into the study. The study protocol provides further detail on study rationale, randomization, data collection and sample size calculation.

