3.5.2. Analysis of secondary outcomes

Secondary outcomes will be compared between groups based on the complete data only. Data will be analyzed on an individual-level.

Table 2 provides the proposed analyses for each of the primary and secondary trial outcomes. These analyses will be adjusted for the baseline term of the variable, education and food insecurity.

Table 2: Analysis Methods for trial outcomes

Intention to treat analysis: Primary outcomes			
	Measure	Method of scaling	Proposed analysis
Physical IPV at 24 months	WHO	Binary (never vs once or more)	GEE, odds ratios
Sexual IPV at 24 months	WHO	Binary (never vs once or more)	GEE, odds ratios
Severe IPV at 24 months	WHO	Binary (never or once vs more than once)	GEE, odds ratios
Controlling behaviours at 24 months	Modified SRPS	Mean	Mixed effects linear regression, mean difference
Earnings in the past month at 24 months		Mean	Mixed effects linear regression, mean difference
Intention to treat analysis: Secondary outcomes			
	Measure	Type of variable	Proposed analysis
Gender attitudes at 24 months	Modified GEMS	Mean	Mixed effects linear regression, mean difference
Depressive symptomology at 24 months	CESD	Mean	Mixed effects linear regression, mean difference
Suicidal ideation at 24 months		Binary	GEE, odds ratios
Life circumstances at 24 months		Mean	Mixed effects linear regression, mean difference
Problem alcohol use at 24 months	AUDIT	Mean and binary (cut-off at 7/8)	Mixed effects linear regression, mean difference And GEE, odds ratios
Quarreling about alcohol at 24 months		Binary	GEE, odds ratios
Last sexual partner at 24 months		Binary (main vs other partners)	GEE, odds ratios
Transactional sex at 24 months		Binary (never vs once or more)	GEE, odds ratios
Work shame at 24 months		Mean	Mixed effects linear regression, mean difference
Work stress at 24 months		Mean	Mixed effects linear regression, mean difference

Stealing because of hunger at 24 months		Binary (never stolen vs once or more)	GEE, odds ratios
Mobilization at cash in emergencies at 24 months		Binary (very difficult/somewhat difficult vs fairly easy/easy)	GEE, odds ratios

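### SAP 3.5.1 names no small-sample variance, degrees of freedom or reference distribution for the GEE on 34 clusters; if z is used, the 5% test rejects about 6.4-7.0% under the null

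*SAP*

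**What the plan says.** SAP 3.5.1 gives the method for binary primary outcomes: "generalized estimating equations (GEE) will be used with an exchangeable correlation matrix and robust standard errors". SAP 3.2 makes tests two-sided and adds: "The statistical significance level set will be at the 5% level". SAP 3.3 states the aim: "All comparative analyses will allow for the clustered nature of the data to ensure correct confidence intervals and type I error rates are calculated". It also promises exact p-values, which does not identify a reference distribution.

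The covariates appear just before Table 2 in SAP 3.5.2, a table that covers primary and secondary outcomes: "These analyses will be adjusted for the baseline term of the variable, education and food insecurity". Time is not among them, yet SAP 3.3 says: "Time will also need to be adjusted for since intervention and control clusters were not measured concurrently". The reason is in SAP 2.1: "16 control clusters had data collected September 2015-December 2015, while 1 control cluster had data collected in August 2016", while the intervention clusters were measured in two phases, January-February 2016 and August-September 2016.

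For missing cases, SAP 3.4 uses multiple imputation up to 25%; above that, "we will use inverse probability weighting to deal with missing data". SAP 3.5.3 adds cluster-level summaries as a sensitivity analysis.

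On the number of clusters, SAP 2.1 gives 34 randomised 1:1 and protocol 7.7 gives 17 per arm. SAP 3.5.1 also mentions 17-22 clusters between arms, which does not fit 34 and may refer to cluster size.

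**The concern.** A robust variance is built from cluster-level residuals. With few clusters, each cluster pulls the fit towards itself, so its residuals are too small and the variance is biased downward. Referring the statistic to z also ignores that this variance is estimated from 34 clusters. Both errors make intervals too narrow.

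Three binary outcomes (physical, sexual and severe IPV) in two sexes give six primary tests. If the usual z default is taken, a borderline IPV result could be called significant for this reason alone, and the correct type I error that SAP 3.3 aims for is not secured. While the choice is open, it could also be made after the results are known.

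**Working it through.** **Inputs.** Two-sided 5% (SAP 3.2). 17 + 17 clusters (SAP 2.1, protocol 7.7). Protocol 7.7.1 plans for 14 of 20 followed per cluster and sex; 10-18 were simulated. Coefficient of variation k = 0.2 (protocol 7.7.1), varied 0.1-0.3. Prevalence 0.35, varied 0.20-0.45. Three covariates (SAP 3.5.2). *Assumed:* the z reference and beta-distributed cluster prevalences.

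**Formulas.** The robust variance is B⁻¹(Σ DᵢᵀWᵢrᵢrᵢᵀWᵢDᵢ)B⁻¹, with B = Σ DᵢᵀWᵢDᵢ and Wᵢ the inverse working covariance. Kauermann-Carroll (KC) replaces rᵢ by (I−Hᵢᵢ)^(−1/2) rᵢ. Mancl-DeRouen (MD) replaces it by (I−Hᵢᵢ)⁻¹ rᵢ. Hᵢᵢ is the cluster's leverage block.

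**Step 1: hand check.** Take the simplest analogue, a comparison of 17 + 17 cluster means. The plan's 5% is reproduced with an unbiased variance and t on 32 df: P(|t₃₂| > 2.037) = 5.0%. The uncorrected sandwich divides each arm's sum of squares by 17² instead of 17 × 16. Its variance is therefore 16/17 = 0.941 of the truth, and its SE √0.941 = 0.970 of the truth. Then:

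- Robust, z: P(|t₃₂| > 1.960 × 0.970 = 1.901) = 6.6%.
- Robust, t₃₂: P(|t₃₂| > 2.037 × 0.970 = 1.976) = 5.7%.
- KC, t₃₂ (squared residuals × 17/16): 5.0%.
- MD, t₃₂ (squared residuals × (17/16)²): P(|t₃₂| > 2.037/0.970 = 2.100) = 4.4%.

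The z reference alone gives P(|t₃₂| > 1.960) = 5.9%. So about 0.9 of the 1.6-point excess comes from z and the rest from the variance.

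**Step 2: simulation of the planned GEE, no time term.** 20,000 null trials per scenario. Monte Carlo SE = √(0.065 × 0.935/20,000) = 0.17 points. Rejection, %:

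| Model | Robust z | Robust t₃₂ | KC t₃₂ | MD t₃₂ |
|---|---|---|---|---|
| Unweighted, 7 scenarios | 6.44-6.87 | 5.50-5.97 | 4.74-5.17 | 4.04-4.40 |
| Weighted, 27-30% loss, 4 scenarios | 6.68-7.04 | 5.73-6.09 | 5.05-5.22 | 4.25-4.47 |

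Weights were treated as known. Scaling the sandwich by G/(G−1) (G = number of clusters) with t₃₂ gives 5.2-5.7%. Repeating the work with logit-normal cluster effects gave 6.4-7.1% with z and 5.5-6.0% with t₃₂. One further check with z gave 7.3%. At 44 clusters, the largest count that the 17-22 phrase could imply, z still rejects 6.2%.

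**Step 3: which missing-data branch.** The protocol's planned loss is 1 − 14/20 = 30%, above 25%, so weighting applies. Pilot retention of 88% at 12 months (protocol 6.3) would mean 12% missing, so imputation is also possible. That branch was not simulated.

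**Step 4: one time term (medium confidence).** The split of the 17 intervention clusters by phase and the coding of time are not given. Baseline dates stand in for 24-month dates. 10,000 null trials each, early/late or linear month. Rejection, %:

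| Phase 1/phase 2 split | Robust z | MD t₃₁ |
|---|---|---|
| 7/10 to 15/2 | 7.0-9.7 | 3.7-5.3 |
| 5/12 | 10.4-11.9 | 5.2-5.9 |
| 3/14 | 14.3-14.9 | 6.7-6.8 |

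A repeat with linear time at an 8/9 split gave 10-11% with z. A three-period factor rejects about 55-57% with z, because the arm contrast then rests on the single late control cluster. That cluster has leverage 1, so the MD variance is undefined.

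**The case against.** The SAP does not choose z; it is silent. With t on 32 df the rate is 5.5-6.1%, and with G/(G−1) scaling 5.2-5.7%. Robust GEE is a standard choice, and the cluster-level summaries in SAP 3.5.3 would help expose a borderline result. On this view the point is a request for clarification. Much of that stands: the excess is modest and conditional. But one unstated choice moves the rate between about 5.2% and 7.0%, and a sensitivity analysis does not set the primary p-value or interval.

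A reader might infer that all six primary tests will have intervals that are too narrow. The documents do not support that without conditions: it needs the z assumption, and it has not been shown under multiple imputation.

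A reader might also take the time-term rates as established. They rest on an unknown phase split, an unknown coding and baseline dates used as a proxy. Nor is growth certain: with an early/late term at 13/4 or 15/2, z rejects about 7.0%, no more than the weighted model without time. For the same reason a flat ban on three periods goes too far. The problem arises if 24-month timing mirrors baseline timing.

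**Conclusion.** The omission is real and should be corrected. With uncorrected robust standard errors and an assumed z reference, the complete-data or weighted GEE without time rejects about 6.4-7.0% under the null. Nominal 95% intervals then cover about 93-94%. With t on 32 df the excess is about 0.5-1 point. Confidence in these figures is high, since the hand calculation and simulations with different cluster models agree. Nothing is claimed for the imputation branch or for the mixed linear models.

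The conflict between SAP 3.3 and 3.5.2 over time is plain in the text. Its numerical effect is held with medium confidence only: about 7-10% with z at most assumed splits, and more if there are few phase 1 clusters.

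**What to change.** **Main change.** State in SAP 3.2 and 3.5.1 a bias-corrected sandwich with a t reference. Kauermann-Carroll with t on 32 df gives about 4.7-5.3%. Mancl-DeRouen with t on 32 df is slightly conservative at about 4.0-4.5%. Apply the same variance to the weighted GEE, and within each imputed data set before pooling if imputation is used. Keep the cluster-level summaries of SAP 3.5.3 as the check.

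**Time.** Reconcile SAP 3.3 with 3.5.2. If time stays in the primary model, fix it as one single-parameter term (an early/late indicator split at August 2016, or linear calendar month) and use Mancl-DeRouen with t on 31 df. This still leaves 5.2-6.8% at the 5/12 and 3/14 splits. Avoid a three-period factor if 24-month timing mirrors baseline timing.

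**Cost.** SAP wording and a software option or short routine. Without time, intervals widen against uncorrected z by 7-8% (Kauermann-Carroll) or 11-12% (Mancl-DeRouen). The hand check gives (2.037/1.960)/0.970 = 1.07 and (2.037/1.960)/0.941 = 1.10. In the protocol's 36 vs 29 and 45 vs 36 scenarios, simulated power falls from about 0.33-0.43 to 0.28-0.38 (Kauermann-Carroll) or 0.26-0.36 (Mancl-DeRouen), partly because false excess is removed. The distance of all these values from the protocol's 80% is a separate matter. With one time term, Mancl-DeRouen with t on 31 df widens intervals by 15-22% at splits 7/10 to 15/2, 25-27% at 5/12 and 37-39% at 3/14.

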3.5.2. Analysis of secondary outcomes

Secondary outcomes will be compared between groups based on the complete data only. Data will be analyzed on an individual-level.

Table 2 provides the proposed analyses for each of the primary and secondary trial outcomes. These analyses will be adjusted for the baseline term of the variable, education and food insecurity.

Table 2: Analysis Methods for trial outcomes

Intention to treat analysis: Primary outcomes			
	Measure	Method of scaling	Proposed analysis
Physical IPV at 24 months	WHO	Binary (never vs once or more)	GEE, odds ratios
Sexual IPV at 24 months	WHO	Binary (never vs once or more)	GEE, odds ratios
Severe IPV at 24 months	WHO	Binary (never or once vs more than once)	GEE, odds ratios
Controlling behaviours at 24 months	Modified SRPS	Mean	Mixed effects linear regression, mean difference
Earnings in the past month at 24 months		Mean	Mixed effects linear regression, mean difference
Intention to treat analysis: Secondary outcomes			
	Measure	Type of variable	Proposed analysis
Gender attitudes at 24 months	Modified GEMS	Mean	Mixed effects linear regression, mean difference
Depressive symptomology at 24 months	CESD	Mean	Mixed effects linear regression, mean difference
Suicidal ideation at 24 months		Binary	GEE, odds ratios
Life circumstances at 24 months		Mean	Mixed effects linear regression, mean difference
Problem alcohol use at 24 months	AUDIT	Mean and binary (cut-off at 7/8)	Mixed effects linear regression, mean difference And GEE, odds ratios
Quarreling about alcohol at 24 months		Binary	GEE, odds ratios
Last sexual partner at 24 months		Binary (main vs other partners)	GEE, odds ratios
Transactional sex at 24 months		Binary (never vs once or more)	GEE, odds ratios
Work shame at 24 months		Mean	Mixed effects linear regression, mean difference
Work stress at 24 months		Mean	Mixed effects linear regression, mean difference

Stealing because of hunger at 24 months		Binary (never stolen vs once or more)	GEE, odds ratios
Mobilization at cash in emergencies at 24 months		Binary (very difficult/somewhat difficult vs fairly easy/easy)	GEE, odds ratios

3.5.3. Additional analyses

To assess the intervention effects at 12 months and 24 months, we will use a mixed effects model at both the cluster and individual level. A sensitivity analysis will be done by performing the analyses with GEE and cluster-level summaries.
